10.6.1 Vital Signs

Vital signs (BP, HR) will be taken in the supine position at Baseline (pre-dose), at the completion of drug infusion, 24 Hours, 48 Hours and Day 5/discharge. Temperature will be taken at baseline per standard of care and reported on the CRF if available. The Investigator will review the pre and post drug infusion vital signs.

If estimated weight was collected at randomization, the subject's actual weight will be measured in hospital using standard hospital scales (i.e., stand up or in-bed scales if the subject is not ambulatory), as soon as possible, but within five days. If actual weight cannot be measured for any reason (due to, for example severe illness or unavailability of in-bed scales at the site), weight will be determined by first asking the subject, second asking a family member or third by estimation.

10.6.2 Biochemistry and Hematology

Blood work will be taken at baseline and at 24 hours including: CBC (hemoglobin, platelets and hematocrit), electrolytes (sodium, potassium, chloride), INR, aPTT, serum creatinine and serum glucose. This is described in [Sections 8.6. , 8.11](#) and the Schedule of Assessments.

If the subject is female and is of childbearing potential, a pregnancy test (urine or serum point-of-care pregnancy test) must be completed. Clinically significant laboratory findings from the 24-hour sample (post dose) will be recorded on the e-CRF as AEs.

10.7 12-Lead Electrocardiogram Monitoring.

A 12-lead ECG will be performed at Baseline or, if the treating physician deems that an ECG will impede the subject's access to care, within 6 hours of randomization, and at approximately 24 Hours. Clinically significant findings on the 24-hour ECG will be recorded on the e-CRF as AEs.

10.8 Concomitant Medications

Concomitant medications (Conmeds) will be collected from the time of randomization to the Day 30 Visit/contact. Conmed identification may be collected via acute stroke hospital patient records or verbal histories from the subject or LAR. Conmeds received while the subject is admitted to the acute stroke hospital will be identified from both hospital records and verbal histories.

After discharge from the acute stroke hospital and for the Day 30 visit, the subject (or LAR if the subject is not able to respond to the questions) will be asked about medications taken since the last contact. Conmeds that were ongoing at the last contact will be updated with a stop date or confirmed as ongoing at Day 30.

10.9 Safety and Data Review

In addition to the site investigator's review and IDMC reviews, on a regular basis the sponsor and external medical monitor will conduct a blinded safety and data review of the subject data collected to date in accordance with the Sponsor's Safety Management Plan.

10.10 Follow-up and Reporting of Pregnancies

Pregnancy is an exclusion criterion for enrolment in this study, but a subject could potentially become pregnant during her participation. All pregnancy cases should be reported if they occurred during the study. To report the pregnancy case, the Investigator must fill out a Pregnancy Reporting Form and inform the Sponsor within one month of identifying a pregnancy case. Study staff must then maintain contact with the subject to obtain information about the outcome—i.e., details about the delivery and the newborn, or about pregnancy termination—and must update the Pregnancy Reporting Form. This information should be provided to the Sponsor within one month of delivery.

Pregnancy itself is not considered an AE, but any complications during pregnancy are to be considered as AEs, and in some cases, could be considered SAEs. Spontaneous abortions, fetal death, stillbirth, and congenital anomalies reported in the baby are always considered as SAEs,

and the information should be provided to the Sponsor regardless of when the SAE occurs (e.g., even after the end of the trial).

11 STATISTICS

11.1 Sample Size Considerations

Assuming a 52% overall responder rate for the placebo group, there will be an approximately 80% power to detect an 8.7% absolute effect difference between response rate (proportion of responders, with Day 90 mRS in the range 0 to 2) with NA-1 and placebo, at alpha level 0.05, 2-sided with a planned sample size of 1076 evaluable subjects, randomized 1:1, per group, accounting for a single interim analysis when 600 subject have reached their primary endpoint assessments, with O'Brien-Fleming alpha-spending function (EaST® V6.3) stopping boundary for overwhelming efficacy and a non-binding 1% conditional power futility stopping boundary. The sample size will be inflated approximately 4% to N= 560 per group to account for loss-to-follow-up and drop-outs.

11.2 Analysis Populations

11.2.1 ITT Population

The primary efficacy analysis will be conducted in the ITT population, defined as all subjects randomized into the trial with grouping by randomized treatment, regardless of treatment actually received. Deceased subject will be included in the ITT population with a mRS score of 6. An ITT analysis will also be conducted for the secondary endpoints, with subject grouped according to the randomized (intended) treatment.

11.2.2 Per Protocol Population

The primary analysis will be repeated on the Per Protocol (PP) population, defined to be all subjects randomized and treated, with no major protocol deviations. This population will be determined via blinded review of protocol deviations at the end of the trial before database lock and unblinding.

Prior to unblinding, the imaging from each subject at the time of inclusion will be adjudicated to determine whether they have met the criteria for endovascular intervention, and hence for the trial. This will include review of baseline NCCT and CTA. Subjects who do not meet the imaging criteria outlined in the trial inclusion/exclusion criteria, will not be included in the Per Protocol (PP) population.

11.3 Analysis of Primary Efficacy Outcome

The primary efficacy outcome for the pivotal assessment of efficacy for regulatory purposes is the overall proportion subjects experiencing a favorable functional outcome 90-days post-randomization, defined as 0 to 2 on the mRS. These subjects are defined as responders. Subjects missing the day 90 primary assessment for any reason will be considered non-responders for the primary analysis (see [Section 11.8](#)). The primary hypothesis to be tested is that administration of NA-1 will result in an increase in the proportion of subjects with independent functioning on the mRS (as defined by a score of 0-2) at Day 90. The primary analysis will be a Wald test for treatment group difference in the primary outcome from a logistic regression adjusted for the 2 stratification variables (alteplase use, first declared thrombectomy device) and the 6 covariates used in the minimization: Age, sex, baseline NIHSS score, baseline ASPECTS score, occlusion

location and site. This will be conducted on the ITT population at the 2-sided 5% significance level overall (for the trial), adjusted for the interim analysis per the O'Brien-Fleming boundary spending function.

[figure not shown]
Three supportive analyses to the primary analysis will be conducted: (1) the primary analysis reapplied to the Per Protocol population; (2) a re-randomization analysis to demonstrate that minimization did not bias the primary endpoint analysis and (3) The primary analysis will be repeated on the PP population using actual first endovascular approach (instead of declared approach). Details of these are provided in the Statistical Analysis Plan.

11.4 Key Secondary Outcome Analysis

The study will also test the secondary hypothesis that among randomized subject, those who are treated with NA-1 will show shift in the distribution of scores on the mRS scale at 90 days, assuming that categories 5 and 6 (bedbound with severe disability, and death) are collapsed. This secondary outcome will use an adjusted proportional odds model to derive the common odds of improvement ("shift") along the mRS scale. Adjustment will include all of the variables in the stratification and minimization algorithm (age, sex, baseline NIHSS score, baseline ASPECTS score, occlusion location, intravenous alteplase treatment, declared first endovascular approach used and site). The proportional odds assumption will be tested.

The choice of the shift analysis is based upon empirical evidence that the mRS scale, when categories 5 and 6 are combined, is a true interval scale meaning that any one step increment in the scale is the same; thus, it is unlikely that the proportional odds assumption will be violated and clinical step changes across the scale are meaningful.⁴² The proportional odds approach to analysis of the mRS scale was applied in the ESCAPE trial.^{3,43} It allows us to include elderly subject (who have a poorer prognosis irrespective of treatment) because a shift from severe to moderate disability will still be recognized as an important outcome.

Figure 2: Projected outcome by mRS category based data from the ESCAPE trial and estimation of NA-1 effect based on the minimal clinically important difference.

Predicted outcomes by mRS category in the control group are from the ESCAPE trial.³ This shows an average 2-3% improvement in outcomes within each mRS category.

If the distribution of subject follows that shown in Figure 2 (i.e. optimally shows a shift across the full scale with common OR 1.32), simulation (n=5000 iterations) demonstrates that the power will be 97.2% to show a common OR of 1.32 with 1076 evaluable subject.

All tests will be conducted with two-sided level of significance $\alpha = 0.05$. A fixed sequence multiple testing procedure will control the overall experiment-wise error rate for the trial (see below). It pre-specifies that, with all tests conducted at the same pre-specified significance level, the primary endpoint will be tested first and all subsequent tests are considered failed and deemed exploratory if conducted, in the order specified (primary analysis first, key secondary analysis second, etc.), after the first test which fails.: All tests after the first failed test are considered exploratory. For the purpose of clarity, since the key secondary analysis of the ordinal mRS scores will employ a proportional odds model (POM), if the proportional odds assumption fails, this key secondary analysis will not be performed, and the remaining secondary tests will still be considered to be protected.

The fixed sequential order for testing in the ITT trial population is:

- 1) Primary efficacy outcome
- 2) Key secondary outcome analysis (shift analysis using proportional odds model);
- 3) Secondary efficacy endpoints, as specified in the order presented below in [Section 11.5](#).

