1.4 Sample Size Determination

Assuming a 52% overall responder rate for the placebo group, there will be 81.7% power to detect an 8.7% absolute effect difference between response rate (proportion of responders, with Day 90 mRS in the range 0 to 2) with NA-1 and placebo, at alpha level 0.05, 2-sided with a planned sample size of 1076 evaluable subjects, randomized 1:1, per group, accounting for a single interim analysis when 600 subject have reached their primary endpoint assessments, with O'Brien-Fleming alpha-spending function (EaST[®] V6.3) stopping boundary for overwhelming efficacy and a non-binding 1% conditional power futility stopping boundary. (See [Section 3.0](#) for further details on the interim analysis.) The sample size will be inflated approximately 4% to N= 560 per group to account for loss-to-follow-up and dropouts.

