- b. The proportion of subjects with $mRS \leq 1$ vs. the proportion with $mRS > 1$**
- c. The proportion of subjects with $mRS \leq 2$ vs. the proportion with $mRS > 2$**
- d. The proportion of subjects with $mRS \leq 3$ vs. the proportion with $mRS > 3$
- e. The proportion of subjects with $mRS \leq 4$ vs. the proportion with $mRS > 4$

This means that regardless of how one chooses to dichotomize the mRS scale, the ratio of the odds of an NA-1-treated subject’s being in the higher functioning category of the dichotomy to a control subject’s odds, will remain the same over the entire span of the mRS scale. Thus, there is no advantage to estimating ORs singly for any of the above dichotomies. If the PO assumption holds, none of them will be significantly different from the common odds ratio. This is analogous to the proportional hazard assumption of the Cox regression model, which posits a constant ratio of treatment vs. control hazard rates at every time point in a study.

Note that the model tests and estimates associated with endpoints “b” and “c” are the more commonly used (and less efficient) mRS dichotomies that represent “good” vs. “poor” functioning. Thus, in addition to providing a statistically powerful test for a treatment vs. placebo shift across all the mRS scores, the POM subsumes the more

common dichotomous mRS analyses that efficacy decisions in stroke trials are often based on (Agresti 2007; Nunn 2016).^[13, 14]

The results of the PO assumption tests, the common odds ratio estimate (with Wald 95% C.I.s) and corresponding Wald test statistics will be summarized in a table. Actual proportions in each category of the collapsed mRS scale with corresponding stacked bar charts will also be presented.

In the event that the test of the PO assumption, needed to proceed with the key secondary efficacy analysis described, determines that the assumption is invalid, this analysis will not be conducted and remaining secondary endpoints to be tested as listed in [Section 7.2.2 to 7.2.5](#) will still be considered to be protected (overall trial alpha still controlled).

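### The 97.2% power stated for the mRS shift analysis is not reached with 1076 subjects: at a common OR of 1.32 the unadjusted ceiling is about 74%, and the fixed sequence lowers the confirmatory power further

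*Protocol*

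**What the plan says.** **Primary.** Protocol 11.1 sizes the trial on mRS 0-2 at Day 90. It takes 52% as the responder proportion on placebo. Its power statement reads "there will be an approximately 80% power to detect an 8.7% absolute effect difference between response rate", and it gives the test level and sample size as "at alpha level 0.05, 2-sided with a planned sample size of 1076 evaluable subjects, randomized 1:1, per group". SAP 1.4 gives the same effect with a sharper figure: "there will be 81.7% power to detect an 8.7% absolute effect difference between response rate". Both allow for one O'Brien-Fleming-type look at 600 subjects and a non-binding 1% conditional-power futility rule. SAP 3.0 puts the one-sided levels at 0.003 (interim) and 0.024 (final).

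**Key secondary.** Protocol 11.4 analyses the same Day 90 mRS with a proportional odds model, with categories 5 and 6 merged. If outcomes follow Figure 2, which "optimally shows a shift across the full scale with common OR 1.32", a simulation of 5000 iterations is said to give 97.2% power with 1076 evaluable subjects. Figure 2 is not shown in the available text. Its caption links the NA-1 effect to the minimal clinically important difference, and the text describes an average gain of 2-3% within each mRS category. Protocol 11.4 regards a violation of proportional odds as unlikely. SAP 7.2.1 explains what the assumption implies: "This means that regardless of how one chooses to dichotomize the mRS scale", the odds ratio is the same.

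**Order of testing.** Under Protocol 11.4, "the primary endpoint will be tested first and all subsequent tests are considered failed" after the first failure. The shift test is skipped if proportional odds is rejected; SAP 7.2.1 sets that check as a score test at 0.15.

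**The concern.** A power of 97.2% tells the sponsor and the monitoring committee that the key secondary is nearly certain to succeed at the projected effect. Three features of the plan argue against that. The odds ratio is modest for 1076 subjects in total. The figure is for a stand-alone test, while the plan lets the shift result count only after the primary has passed. And the primary's 8.7 points corresponds to a larger odds ratio at the 0-2 cut than 1.32.

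Type I error is not affected. What is at stake is whether the stated chance of a confirmatory shift result is right, and whether the reader can tell what NA-1 effect the two endpoints share.

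**Working it through.** **Inputs.** Placebo 52%, difference 8.7 points, 1076 evaluable (Protocol 11.1). I read 1076 as the total, 538 per arm, because it is inflated by about 4% to 560 per group. Interim at 600/1076 = 55.8% information. Common OR 1.32, six categories, 97.2% (Protocol 11.4). Pre-test level 0.15 (SAP 7.2.1).

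**1. Reproduce the primary.**
- OR at the 0-2 cut: (0.607/0.393)/(0.52/0.48) = 1.43.
- Drift: 0.087/√[(0.52×0.48 + 0.607×0.393)/538] = 2.888.
- O'Brien-Fleming-type spending at 55.8% information gives one-sided levels of 0.0027 and 0.0241 (final z 1.975), which agree with SAP 3.0.
- Two-look power is 81.6% with the futility stop and 82.1% without. The SAP's 81.7% reproduces, with no covariate adjustment.

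**2. Try to reproduce 97.2%.** For a proportional odds comparison with 1:1 allocation, Whitehead's approximation is

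power = Φ( ln(OR) × √[N(1 − Σp³)/12] − 1.96 ),

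where p are the category proportions averaged over the arms. With six categories, 1 − Σp³ is largest when all are equal: 1 − 6×(1/6)³ = 0.972. This gives a ceiling for any distribution.

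| Total N | ln(1.32) × √[N×0.972/12] | Power ceiling |
|---|---|---|
| 1076 | 0.2776 × 9.337 = 2.592 | 73.6% |
| 2152 | 0.2776 × 13.204 = 3.666 | 95.6% |

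Simulation with three assumed placebo distributions, each with 52% at mRS 0-2, gives 73-74% at 538 per arm. Seven categories instead of six would give 74.0%, and a one-sided 0.05 test 82.8%. To reach 97.2%, ln(OR) × √[N×0.972/12] must equal 1.96 + 1.91 = 3.87. That needs a common OR of about 1.51 at N = 1076, or about 2400 subjects at OR 1.32.

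**3. Effect of the sequence.** The shift test is confirmatory only if the primary passes, so P(shift confirmed) ≤ P(primary passes). Suppose OR 1.32 holds exactly at the 0-2 cut:
- Placebo odds 0.52/0.48 = 1.0833; times 1.32 = 1.43; 1.43/2.43 = 58.85%, a gain of 6.85 points.
- Drift 0.0685/√[(0.52×0.48 + 0.5885×0.4115)/538] = 2.265.
- Two-look primary power is 61.1% with futility and 61.7% without. It stays at about 60-62% for assumed placebo rates of 45-55%.
- Simulated probability that primary and shift are both significant: about 58% (unadjusted, no interim look, final-analysis critical values).
- A 0.15-level pre-test rejects a true proportional odds assumption about 15% of the time. Treating it as roughly independent of the other two tests, 0.58 × 0.85 ≈ 0.49, so the chance of passing the whole written sequence is roughly 50%.

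**4. Can Figure 2 hold both effects?** The text's 2-3% per category, summed over mRS 0, 1 and 2, is 6-9 points. At 2.9 points each it is exactly 8.7. With assumed control distributions at 52% in mRS 0-2, and matching losses in the worse categories, the OR is 1.43 at the 0-2 cut, about 1.2-1.3 at the others, and the fitted common OR is about 1.3 (1.28-1.34). Even at 1.34 the ceiling in step 2 is Φ(0.2927×9.337 − 1.96) = 78%, so this reading does not rescue 97.2%.

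**The case against.** **The plan may hold one effect, not two.** A reader might infer that the primary and the key secondary were planned for contradictory NA-1 effects. The documents do not establish this. Figure 2 is not shown, and step 4 shows that one projection can carry both 8.7 points and an average OR near 1.32. Nor does any section say that 1.32 is the effect on which the trial is sized, or claim about 80% primary power at that value. This objection stands. What remains is that the odds ratios would then differ across cuts, which sits poorly with the expectation that proportional odds will hold.

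**Covariate adjustment may raise power.** It may, somewhat. But reaching 97.2% at OR 1.32 would require adjustment to act like 2400/1076 ≈ 2.2 times the sample. The primary's own figure reproduces unadjusted, and Protocol 11.4 mentions no covariates in describing the simulation.

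**Stand-alone power for a secondary is common practice, and every fixed sequence caps later tests.** True, and the sequence itself is no fault. Most of the gap between 97.2% and 58% is not due to it: about 23 points (97.2 to 74) are the stand-alone figure and about 16 (74 to 58) the gate. The stand-alone figure needs correcting whatever one thinks of the gate.

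**The cause looks obvious.** A reader might infer from "at alpha level 0.05, 2-sided with a planned sample size of 1076 evaluable subjects, randomized 1:1, per group" that 1076 per arm was simulated. That is possible, but 2152 subjects give 95.6% at best by this approximation, not 97.2%, and the inputs are not stated. It remains a guess.

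**Conclusion.** The point holds as an error in a stated power. Unadjusted, with 538 per arm and two-sided 0.05, the shift test at a common OR of 1.32 has at most about 74% stand-alone power, against 97.2% printed. The ceiling does not depend on the unseen Figure 2 distribution, only on six categories, 1:1 allocation and 1076 in total.

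That the confirmatory power of the shift test cannot exceed the primary's is a matter of logic. Its size depends on the effect at the 0-2 cut: about 61% for the primary and 58% for both if OR 1.32 applies there exactly with 52% on placebo, less once the proportional-odds pre-test is counted. It would be wrong to read the 61% as refuting the plan's primary power, which is stated for 8.7 points and is correct there.

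**What to change.** - Rerun the simulation with 538 per arm, from one stated set of placebo and NA-1 mRS distributions used for both endpoints.
- In Protocol 11.4, replace 97.2% with the resulting stand-alone power, stating N per arm, sidedness and whether the model is adjusted.
- Beside it, give the probability of passing the written sequence: primary significant, proportional odds retained at 0.15, and shift significant.
- State the odds ratio and point difference at the 0-2 cut that Figure 2 implies, and the primary's power at that effect, and cross-refer from Protocol 11.1 and SAP 1.4. If the odds ratios differ across cuts, say so and reconcile this with the expectation of proportional odds.

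The cost is one simulation rerun and a few sentences. Sample size, tests, alpha and conduct do not change. The drawback is that the stated power of the key secondary becomes less favourable.

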6 TRIAL DESIGN

This is a Phase 3 randomized, multicentre, blinded, placebo-controlled, parallel group, single-dose design. Subjects harboring an acute stroke and who are selected for endovascular revascularization in accordance with local institutional practices and who harbor a small established infarct core and with good collateral circulation will be given a single, 2.6 mg/kg (up to a maximum dose of 270 mg) intravenous dose of NA-1 or placebo as soon as they are deemed to have met the enrollment criteria and with the intention of starting administration within 30 minutes of randomization.

A total of 1120 subjects aged 18 years and older will be enrolled into the study. All subjects will be followed for 90 days (or until death if prior to 90 days). Further details on the study procedures can be found in [Table 2-1: Schedule of Assessments](#). The end of study is defined as the date that the last enrolled subject has completed their Day 90 visit.

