6.2 Randomization and Blinding

Treatment will be assigned using 1:1 randomization (placebo:NA-1) centrally, using a web-based algorithm with treatment assignment allocated by web-based real-time interaction with the site. Randomization will be fully concealed by having both dynamic real-time allocation based upon random number generation and visually identical appearing NA-1 and placebo vials. All vials will have a unique vial number.

In order to minimize differences between the two treatment arms of the trial other than the investigational treatment, the protocol will restrict the use of multiple non-randomized intra-arterial therapies and stratify randomization by (a) use of intravenous thrombolysis with alteplase (yes/no) and (b) the declared first thrombectomy approach. The intended first thrombectomy approach will be restricted to the use of either a stent retriever or clot aspiration device. The intent to use any other endovascular device type or intra-arterial medications as the initial thrombectomy approach constitutes an exclusion criterion. Additionally, if intravenous thrombolysis is planned for the subject, the intent to use any intravenous thrombolytic other than alteplase is an exclusion criterion.

Thus, randomization will be stratified by declared first thrombectomy approach which will be dichotomized as stent retriever vs aspiration device, and by intravenous alteplase use (yes/no). Within each stratum, a randomized minimization procedure will occur on 6 baseline prognostic variables. Subject data required for randomization are age, sex, baseline NIHSS scores, baseline ASPECTs score, occlusion location and site.

The purpose of stratification is to provide increased certainty that equal or near-equal proportion of patients in each stratum will receive NA-1 or placebo.

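### The 97.2% power stated for the key secondary mRS shift analysis is not delivered by 1076 subjects at a common odds ratio of 1.32; the design gives about 73%

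*Protocol*

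**What the plan says.** Protocol 11.4 plans a covariate-adjusted proportional odds model for the Day 90 mRS, with scores 5 and 6 merged, which leaves six ordered categories. It posits an effect that "optimally shows a shift across the full scale with common OR 1.32" and reports that "simulation (n=5000 iterations) demonstrates that the power will be 97.2% to show a common OR of 1.32 with 1076 evaluable subject". The same section sets the level: "All tests will be conducted with two-sided level of significance" of 0.05. The shift test stands second in the fixed sequence, after the primary outcome.

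Protocol 11.1 describes a "planned sample size of 1076 evaluable subjects, randomized 1:1, per group", and then: "The sample size will be inflated approximately 4% to N= 560 per group to account for loss-to-follow-up and drop-outs". Section 6 states that "A total of 1120 subjects aged 18 years and older will be enrolled into the study", and section 6.2 that "Treatment will be assigned using 1:1 randomization (placebo:NA-1) centrally". For the primary endpoint, SAP 1.4 gives "81.7% power to detect an 8.7% absolute effect difference" from a placebo rate of 52%. The SAP describes the shift analysis in 7.2.1 but gives no power for it, so the figure in Protocol 11.4 is the only one.

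**The concern.** The two power statements do not sit together. The same 1076 subjects give the primary 81.7% power for 52% against 60.7%, an odds ratio of (0.607/0.393)/(0.52/0.48) = 1.43. Using the full scale gains some efficiency over a single cut, but it should not lift power to 97.2% at the smaller odds ratio of 1.32.

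A stated power of 97.2% means a 2.8% chance of missing a true common odds ratio of 1.32; the recomputed chance is about 26%. A reader who trusts the protocol would take a non-significant shift result as near-exclusion of an effect of that size. The test also gates the protected claims below it in the sequence, unless the proportional odds assumption fails and the test is skipped.

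**Working it through.** **Inputs.** Common odds ratio 1.32, so ln(1.32) = 0.2776; six categories; two-sided alpha 0.05 (all Protocol 11.4). Allocation 1:1 (Protocol 6.2). Placebo responder rate 52% (Protocol 11.1). The control mRS distribution is in Figure 2, which is not available, so the check uses a bound that needs no distribution, plus several assumed distributions.

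**Step 1: is 1076 the total or the arm size?** The inflated size is 560 per arm, and 2 × 560 = 1120, the enrolment total. Also 1076 × 1.04 = 1119. So 1076 is the total, 538 per arm. The primary power agrees: 52% against 60.7% with 538 per arm gives 82.1% at a fixed two-sided 0.05, and 81.7% at the final-analysis level in SAP 3.0 (0.024 one-sided). The SAP's 81.7% reproduces. With 1076 per arm it would be about 98%.

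**Step 2: ceiling on the shift power.** Under proportional odds with equal arms, the information on the log common odds ratio is approximately

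N/12 × (1 − Σ p̄ₖ³),

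where p̄ₖ is the proportion in category k averaged over the arms (Whitehead's formula). It is largest when all k categories are equally filled, where it equals N/12 × (1 − 1/k²).

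- Six categories: z = 0.2776 × √(1076/12 × 35/36) = 2.592; power = Φ(2.592 − 1.960) = 73.6%.
- Unlimited categories: z = 0.2776 × √(1076/12) = 2.629; power = 74.8%.

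**Step 3: assumed distributions.** Four six-category distributions with 52% in mRS 0–2 give 72.8% to 73.5% by the formula. Simulations of 5000 runs each, over several six-category distributions, give 72.6% to 74.7%; the spread around the ceiling is simulation error. The standard error of a 5000-run estimate at 97.2% is √(0.972 × 0.028/5000) = 0.23 points, so chance cannot explain a 24-point gap.

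**Step 4: variants (odds ratio 1.32 unless stated).**

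| Variant | Power |
|---|---|
| 538 per arm, one-sided 0.05 | 82–83% |
| 560 per arm, two-sided 0.05 | about 75% |
| 538 per arm, odds ratio 1.43 | about 91% |
| 1076 per arm, two-sided 0.05 | 95–96% |
| 1076 per arm, one-sided 0.05 | about 97.8% |

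Only an arm size of 1076 comes near the stated figure.

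**Step 5: what 97.2% would need.** The required z is 1.960 + 1.911 = 3.871. With six equal categories, N = 12 × 3.871² / (0.2776² × 35/36) ≈ 2,400 in total (up to about 2,450 for the assumed distributions). With 1076 subjects, the odds ratio must be exp(3.871/√(1076/12 × 35/36)) ≈ 1.51.

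**Step 6: the fixed sequence.** On a 52% placebo rate, an odds ratio of 1.32 gives odds of 1.083 × 1.32 = 1.43, or 58.8% responders: a difference of 6.8 points, not 8.7. Simulated jointly, the primary has about 61% power at its final-analysis level, the shift test about 73%, and both succeed about 58% of the time. These figures assume a control distribution with 52% in mRS 0–2.

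**The case against.** The strongest defence is covariate adjustment. The ceiling applies to an unadjusted comparison, or to an adjusted one if 1.32 is the conditional odds ratio. The planned model is adjusted, whereas 1.32 is attached to a projected outcome distribution, which suggests a marginal odds ratio. On that reading the adjusted test targets a larger conditional odds ratio and gains power: about 85% to 87% with a prognostic score of SD 1.0 on the logit scale, 92% to 93% with SD 1.5, and 98% with SD 2.0 (all assumed values). The last corresponds to covariates explaining about 55% of the latent outcome variance and an adjusted odds ratio of about 1.58. So the shortfall depends on what 1.32 means, and the protocol does not say whether the simulation was adjusted. This does not restore 97.2%, because no document states the covariate strength required. If 1.32 is what the planned model estimates, adjustment does not help (64% to 73% in simulation).

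The explanation by arm size is also unproven. Two-sided, 1076 per arm gives 95.6%, about 7 standard errors below 97.2%; one-sided, 97.8% is more than 2.5 above it and conflicts with the two-sided rule.

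It is fair, too, that the figure sets no sample size, boundary or decision rule, that the planned confidence interval would limit misreading, and that the two endpoints may be powered for different effects. The choice of 1.32 rather than 1.43 is therefore not itself an error. These points limit the consequences; they do not make the stated power correct.

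**Conclusion.** The concern holds. On its stated inputs the shift analysis has about 73% power, not 97.2%. This rests on 1076 being the total, which the enrolment figures and the reproduced primary power both support, and on 1.32 being either the odds ratio of an unadjusted comparison or the conditional odds ratio of the planned model. No mRS distribution changes it materially. A marginal reading narrows the gap but reaches the stated figure only under strong, unstated covariate assumptions. The error is confined to the power statement for the key secondary outcome.

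**What to change.** - Rerun the simulation with 538 per arm. State in Protocol 11.4 the control distribution, whether the model was adjusted, and whether 1.32 is conditional or marginal.
- Replace 97.2% with the result, about 73% on the plain reading. If a marginal odds ratio is intended, state the assumed covariate strength and the conditional odds ratio that follows.
- Delete *per group* after 1076 in the Protocol synopsis, Protocol 11.1 and SAP 1.4.
- Preferably, add the shift power at the primary's own effect (about 91% at an odds ratio of 1.43) and the chance that primary and shift both succeed at 1.32 (about 58%).

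The cost is a short rerun, a wording change and a less favourable stated power. Enrolment, endpoints, alpha and the primary analysis are unaffected.
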